7.2.3 Patients with Depression and Comorbidity Analysis

- To understand the antidepressant choice among Korean patients with depression and other comorbidities (psychiatric comorbidities or mild cognitive impairment (MCI))
- Secondary analysis
- Endpoints:
 - Proportion of 11 antidepressants
 - Choice of study drug
- Population: patients who satisfy the acute treatment phase population and with a prespecified comorbidity
- Significance on continuous variables will be tested by ANOVA (if equal variance condition satisfied) or Kruskal-Wallis H test (otherwise). Provider specialty and other patient characteristics will be used to fit antidepressant choice by multivariate logistic regression analysis of each study drug choice.
- Covariates: antidepressant class covariates such as SSRIs, SNRIs, other ADs will be used as grouping variables.
- Missing values will be dropped from the analysis.

- The role of this analysis is to provide information on antidepressant selection in the acute phase of drug therapy for Korean patients with depression and comorbidity by each comorbidity group.

7.2.4 Relationship between Non-pharmacological Treatments and Antidepressant Compliance Analysis

- To understand the relationship between non-pharmacological treatments and antidepressant compliance among Korean patients with depression
- Secondary analysis
- Endpoints:
 - Medication compliance (adherence, discontinuation, and persistence) by the number of non-pharmacological treatments
- Population: patients who satisfy the acute treatment phase population
- Significance on continuous variables will be tested by ANOVA (if equal variance condition satisfied) or the Kruskal-Wallis H test (otherwise).
- Covariates: antidepressant class covariates such as SSRIs, SNRIs, and other ADs will be used as grouping variables.
- Missing values will be dropped from the analysis.
- The role of this analysis is to provide information on the relationship between non-pharmacological treatments and antidepressant compliance among Korean patients with depression.

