2.2 STUDY OBJECTIVES

Primary objectives:

1. Explore baseline characteristics and drug utilization patterns of 11 commonly used antidepressant therapy during 90 days of acute treatment phase
 - Top 11 commonly used antidepressants according to local market data are as follows:
 - Escitalopram, paroxetine, fluoxetine, mirtazapine, duloxetine, sertraline, venlafaxine, tianeptine, vortioxetine, desvenlafaxine, bupropion
 - Proportion of antidepressants prescribed by sex, age (<20, 21-64, > 65), sex and age combined
 - Initial doses used, average daily doses of each antidepressants
 - Average length of treatment with index medication before therapy change occurs (switching, combination, augmentation, discontinuation)
 - Adherence and persistence measured by medication possession ratio during first 90 days of treatment period
2. Explore drug utilization patterns such as therapy changes, medication compliance and recurrence relationship, and risk of adverse outcomes during maintenance phase
 - The choice of antidepressant, average length of new treatment maintenance, average number of co-administered medications (e.g., atypical antipsychotics, mood stabilizer, thyroid hormone, psychostimulant) when following changes occur from initial monotherapy:
 - Switching
 - Combination
 - Augmentation
 - Medication compliance and recurrence
 - Compliance measured as adherence and persistence
 - Recurrence
 - Relationship between recurrence and compliance

PFIZER CONFIDENTIAL

- *Risk of adverse outcomes measurement between individual ADs that are well known to be treatment-related (e.g., hyponatremia, GI bleeding, fractures, falls, risk of intracranial hemorrhage, attempted suicide/self-harm, myocardial infarction, epilepsy/seizures, stroke/transient ischemic stroke)*

Secondary objectives:

1. *Choice of antidepressants and drug utilization patterns in patients with various comorbidities*
 - *Psychiatric comorbidities*
 - *Mild cognitive impairment (MCI)*
2. *The relationship of non-pharmacologic treatment and discontinuation, medication compliance*
 - *Non-pharmacologic treatments may include: cognitive behavioral therapy (CBT), frequency of physician visit during acute and maintenance phase of treatment*
 - *Frequency of visit during the first 3 months of acute phase and its relationship to treatment maintenance at 4, 5, 6, 7, 8, 9 month time points and discontinuation rate*
3. *Choice of antidepressants by non-psychiatric specialty*

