Persistence	Primary outcome	HIRA Database	
For each of 11 study drugs, the average length of treatment on the index drug during the first 180 day period (allowing 14 day permissible gap) will be calculated
 
Switching, combination, augmentation, discontinuation will terminate the persistent period

Discontinuation	Primary outcome	HIRA Database	For each of 11 study drugs chosen as index drug, the percentage of discontinuation in the first 90 days from the index date (acute treatment phase) will be measured (allowing 14 day permissible gap)
Adherence	Primary outcome	HIRA Database	
For each of 11 study drugs chosen as index drug, adherence will be measured by MPR and persistence during the first 90 day and 180 day period from the index date, respectively (acute treatment phase). MPR ≥ 0.75 and persistence ≥ 90 will be considered as adherence.
 
* For those period with any identified adverse outcome such as GI bleeding will be considered as non-adherent period

Drug utilization pattern in acute phase	Secondary outcome	HIRA Database	
During the first 90 day period starting from the index date, the following types of drug utilization pattern is recorded
 
- monotherapy (kept on the index medication)- switching (switched to other antidepressant)- combination (adding other antidepressant)- augmentation (adding other non-AD drug such as antipsychotic)
Drug utilization pattern in maintenance phase	Secondary outcome	HIRA Database	
During the second 90 day period (91 ~ 180 days) starting from the index date, the following types of drug utilization pattern is recorded
 
- choice of antidepressant- monotherapy (kept on the same medication)- switching (switched to other antidepressant)- combination (adding other antidepressant)- augmentation (adding other non-AD drug such as antipsychotic)

PFIZER CONFIDENTIAL

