Comorbidities	Covariates	HIRA Database	
The following comorbidities which may affect the drug utilization patterns of antidepressants will be operationally defined using KCD-7 diagnosis codes in medical claims
 
 - Psychiatric comorbidities: panic disorder (F41.0), bipolar disorder (F31), PTSD (F43.1), acute stress (F43.0), personality disorder (F60-69), GAD (generalized anxiety disorder) (F41.1), adjustment disorder (F43.2), sleep disorder (F51), g470, f108), dementia (F00-F03, G30), OCD (obsessive compulsive disorder) ((F42), F429, F605, F428), substance related disorders (F10-19), schizophrenia (F20-29), eating disorder (F50), sexual dysfuntion (F52), mental retardation (F70-F79), developmental disorder (F80-F89), somatoform disorder F45, eating disorder F50 - Mild cognitive impairment (MCI): diagnosis code F06.7 along with a procedure code for neurocognitive function test FB001-FB060* - Charlson Comorbidity Index (CCI)
Non-pharmacologic treatments	Covariates	HIRA Database	
The following non-pharmacologic treatments which may affect antidepressant adherence and persistence/discontinuation will be defined using NHI procedure codes* in medical claims
 
 - Individual psychotherapy** NN012 intensive analytic NN013 intensive - Group psychotherapy NN021 general NN022 analytic NN023 psychodrama - Family psychotherapy NN031 individual NN032 group NN040 occupational or recreation therapy NN050 narcoticsynthesis - Electroconvulsive therapy NN071 simple ETC NN072 modified ETC - Continuous sleep treatment NN081 electro sleep treatment NN082 drug induced sleep treatment NN083 sleep treatment with anesthesia NN090 psychiatric rehabilitation NN100 psychiatric emergency treatment - Psychiatric social work NN111 individual history taking NN112 social work guidance NN113 social investigation

PFIZER CONFIDENTIAL

			
NN114 home visiting
 
* Since January 2018, new code system was employed for psychotherapy and expert advisor consensus will be used to align the new codes to the codes above
 
NN001-NN005 individual psychotherapy
 
NN061 Cognitive Behavioral Therapy-Individual
 
NN062 Cognitive Behavioral Therapy-Group
 
** NN011 supportive was excluded since it is more of a routine code used for majority of patients according to Ahn et al. (2012)¹³

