7 STATISTICAL METHODOLOGY AND STATISTICAL ANALYSES

7.1 STATISTICAL METHODS

Means, medians, and standard deviations will be provided for continuous variables when performing descriptive analysis of continuous data. Numbers and percentages will be provided for dichotomous and polychotomous variables when performing descriptive analysis of categorical data. Bivariate comparisons of baseline characteristics and outcomes measures will be provided. Appropriate tests (e.g., t-test, chi-square test) will be used based on the distribution of the measure. The cumulative incidence rate for clinical outcomes (major bleeding event, and stroke) will be calculated. The incidence rate will be calculated as the number of patients who experience the event divided by the observed time at risk. An unadjusted Kaplan Meier curve will be drawn to illustrate time-to-event.

PFIZER CONFIDENTIAL

[figure not shown]
The propensity score matching (PSM) technique and the propensity score weighting technique will be used to control for confounders when comparing the antidepressants. After PSM, no significant differences are expected among all pre-index measures between the antidepressant cohorts except for clinical indication differences. Also covariates in Table 3 will be included in multivariate logistic regression framework for each antidepressant choice (binary variable of 1 for choice and 0 for no choice). Covariates will include variables such as age, geographic region, CCI score, and comorbidities. Non-pharmacologic treatments will be used as a covariate if dependent variable is adherence, persistence, or discontinuation since a previous study reported accompanying number of non-pharmacologic treatments significantly increase adherence of antidepressants (Ahn J et al., 2011). The final lists of variables to be used in the model will be discussed and determined during analysis development, after reviewing the pre-matched descriptive tables and post-matched pre-index measures. All data analysis will be executed using statistical software SAS version 9.4 or later.

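### SAP 7.2.4 compares compliance by a treatment count with no counting window or landmark, so an association can appear even if the treatments have no effect

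*SAP*

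**What the plan says.** SAP 7.2.4 is a secondary analysis with the endpoint "Medication compliance (adherence, discontinuation, and persistence) by the number of non-pharmacological treatments". Its population is everyone in the acute-phase analysis. Continuous outcomes are tested by ANOVA or Kruskal-Wallis, and drug class is the only grouping covariate.

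The exposure is defined in SAP 5.4, Table 3: "The following non-pharmacologic treatments which may affect antidepressant adherence and persistence/discontinuation will be defined using NHI procedure codes* in medical claims". A list of codes follows, with no first day, last day or landmark.

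The outcomes, in SAP 5.1 and Table 3, all run from the index date:
- Persistence is "the average length of treatment on the index drug during the first 180 day period (allowing 14 day permissible gap) will be calculated". It ends at switching, combination, augmentation or discontinuation.
- Discontinuation is assessed over the first 90 days.
- Adherence requires an MPR of at least 0.75 and persistence of at least 90.

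Secondary objective 2 (SAP 2.2, Protocol section 8) also counts "frequency of physician visit during acute and maintenance phase of treatment" as a non-pharmacologic treatment. One sub-item has a time order: "Frequency of visit during the first 3 months of acute phase and its relationship to treatment maintenance" at months 4 to 9. It covers visits only, adds a discontinuation rate without a period, and does not reappear in 7.2.4.

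SAP 7.1 states: "Non-pharmacologic treatments will be used as a covariate if dependent variable is adherence, persistence, or discontinuation". It gives no period for that covariate either.

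**The concern.** A count of sessions taken while the outcome is accruing depends on how long the patient stays in care. A patient who stops on day 20 has had little time to collect sessions on treatment; one who stays to day 180 has had nine times as long. If attendance falls off when the drug period ends, a high count is partly a consequence of long persistence. This is immortal-time bias. ANOVA and Kruskal-Wallis treat the count as if it were known on day 0.

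At stake is a significance-tested finding that more non-pharmacological treatment goes with better compliance, when the design alone could produce it. SAP 7.1 already cites a previous study as showing that such treatments increase adherence, so readers are likely to take a positive result as confirmation. If the same kind of count is used as a covariate in the drug comparisons, it could also absorb part of a real difference between drugs.

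**Working it through.** The documents give no session rate, share of users or expected association, so there is no planned figure to reproduce. The check asks what 7.2.4 would show if sessions had no effect.

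**Assumed inputs, not from the documents.** Time to the end of the index-drug period, T, is exponential with mean 90 days (λ = 1/90). Persistence is P = min(T, 180); the cap is from SAP 5.1. A fraction u of patients use therapy. A user's session count over days 0-180 is Poisson with mean r × [P + c × (180 − P)]. Here r = 1/30 per day and c is the session rate after the drug period ends, relative to the rate before. The true share reaching day 90 is e^(−1) = 36.8%, whatever the number of sessions.

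**Worst case: all use therapy (u = 1), sessions stop with the drug (c = 0).** λ + r = 4/90.
- P(0 sessions) = 0.25 × (1 − e^(−8)) + e^(−8) = 0.2503
- P(0 sessions and T ≥ 90) = 0.25 × (e^(−4) − e^(−8)) + e^(−8) = 0.0048
- Share reaching day 90 with 0 sessions = 0.0048 / 0.2503 = 2%

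Integrating the Poisson probabilities over T in the same way gives 17% for 1-2 sessions and 74% for 3 or more. Mean persistence is about 23, 57 and 128 days. The upward gradient persists for mean times of 60 to 150 days and rates of 1/60 to 1/14 per day.

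**Only 30% use therapy, c = 0.** The zero group is now mostly never-users:
(0.7 × 0.3679 + 0.3 × 0.0048) / (0.7 + 0.3 × 0.2503) = 0.2590 / 0.7751 = 33%.
The other groups contain only users, so they stay at 17% and 74%. The pattern is no longer monotone.

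**What happens to sessions after the drug period ends.** These runs assume 45% on drug at day 90 (λ = −ln 0.45 / 90). That choice is guided by the Protocol section 7 statement that adherence is below 50%.

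| Setting | Result under no effect |
|---|---|
| All users, sessions at half rate afterwards | mean persistence 56, 83, 125 days for 1-2, 3-5, 6+ sessions |
| 30% users, sessions stop | 84 days (0 sessions) vs 162 (6+) |
| 30% users, sessions continue after half of the endings (therapy changes) | 87 days (0) vs 108 (6+) |
| Session rate unchanged | flat, about 90 days in every group |

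Kruskal-Wallis at 0.05 with n = 2,000 and 30% users (1,000 replicates) rejected in 100% of replicates at c = 0 and c = 0.5, 89% at c = 0.8, and 4.8% at c = 1.

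**Would a fixed 0-90 day window be enough?** No. With 45% on drug at day 90, all patients users and c = 0.5, discontinuation by day 90 still runs from 76% (0 sessions) to 29% (6+). With c = 0 it runs from 90% to 16%.

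**Landmark.** Sessions are counted in days 0-30 among patients still on drug at day 30. Mean persistence is then 113 days for 0, 1, 2 and 3+ sessions, and Kruskal-Wallis (30% users) rejects in 5.1% of replicates. This is flat because the count closes before the outcome starts. It shows that the time-related bias goes, not that confounding does.

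**Covariate in SAP 7.1.** Take two drugs whose mean persistence truly differs by about 17 days, and adjust for a session count taken over the outcome period. The difference becomes 6.9 days (all users, sessions stop), 13.9 (all users, half rate) or 15.6 (30% users, sessions stop).

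**The case against.** The strongest reply is that the bias is not inevitable. Persistence in this plan ends at switching, combination or augmentation as well as at stopping, and such patients remain in treatment, so their sessions can continue. If the session rate does not change, the false-positive rate is the nominal one. Table 3 also drops the routine supportive code because most patients have it, which suggests the remaining codes are far from universal. All of this stands. A reader might infer that 7.2.4 is bound to show a benefit, or that 2% against 74% is the expected size. The documents support neither: they give no session rate, no share of users and nothing on attendance after the drug period ends.

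A reader might also infer that SAP 7.1 adjusts the drug comparisons for a post-index count. It states no timing and leaves the final variable list to be settled after post-matching pre-index measures are reviewed. Protocol 9.7 also keeps raw alongside matched results, so unadjusted differences stay visible. The covariate point is therefore conditional.

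The visit sub-objective does put exposure before outcome, but only for visits, and 7.2.4 does not use it. Calling the analysis informative rather than confirmatory lowers the stakes without removing the bias, because it is still significance-tested.

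**Conclusion.** The point holds in conditional form. Exposure and outcome can share the same days, no landmark or time-varying exposure is planned, and the tests cannot separate the two. A spurious association can appear whenever sessions become rarer after the index-drug period ends. Its direction among users follows from the plan's definitions plus that one condition.

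Its size does not follow from the documents. On the assumptions above, the share reaching day 90 with 0 against 3+ sessions ranges from 2% vs 74% (worst case) through 33% vs 74% (30% users) to no difference (session rate unchanged). Even a fall in the session rate to 0.8 gave 89% false positives at n = 2,000.

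This is a should-fix. A reader might go further and treat it as invalidating the study's compliance results. That is not supported: 7.2.4 is secondary, SAP section 3 sets no hypotheses or decision rules, and no primary result depends on it. The primary compliance endpoints are touched only if the SAP 7.1 covariate turns out to be counted over the outcome period.

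**What to change.** In SAP 7.2.4, count sessions in a fixed early window that closes before outcome follow-up starts, for example days 0-30. Measure persistence, discontinuation and adherence after that day, among patients still on the index drug, and restate each outcome's period to match. A fixed window without the on-drug condition is not enough. For time to discontinuation, a time-varying session count is an alternative; it does not directly suit MPR or the binary adherence endpoint. If visit frequency is analysed here too, apply the same rule to its three-month window.

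In SAP 7.1, if non-pharmacologic treatment is a covariate for adherence, persistence or discontinuation, restrict it to pre-index or landmark-window treatment. With the latter, start the outcome at the landmark as well.

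The costs are modest but go beyond wording. Patients who stop before the landmark leave this one analysis. On the illustrative curves with a day-30 landmark that is 1 − 0.45^(1/3) = 23% to 1 − e^(−30/90) = 28%. The estimand becomes conditional on being on drug at the landmark. The SAP was amended during data analysis, so some programs may need rerunning, but the claims dates are already held. The result should still be reported as an association, since a landmark does not remove differences in motivation or severity.

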7.2.5 Selection of Antidepressant by Specialty Analysis

- To understand the antidepressant choice among the Korean providers by specialty
- Secondary analysis
- Endpoints:
 - Proportion of 11 antidepressants by provider specialty
- Population: patients who satisfies the acute treatment phase population and with a prespecified comorbidity
- Significance on continuous variables will be tested by ANOVA (if equal variance condition satisfied) or Kruskal-Wallis H test (otherwise). Provider specialty and other patient characteristics will be used to fit antidepressant choice by multivariate logistic regression analysis of each study drug choice.
- Covariates: antidepressant class covariates such as SSRIs, SNRIs, other ADs will be used as grouping variables. Provider specialty and other patient characteristics will be used to fit antidepressant choice by multivariate logistic regression analysis of each study drug choice.
- Missing values will be dropped from the analysis.
- The role of this analysis is to provide information on antidepressant selection in the acute phase of drug therapy for Korean patients with depression and comorbidity by each comorbidity group.

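### SAP 7.2.4 compares compliance across numbers of non-pharmacological treatments without patient or provider adjustment, does not call the adjusted model that SAP 7.1 foresees, and sets no window for counting treatments

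*SAP*

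**What the plan says.** SAP 7.2.4 is the section for secondary objective 2. Its endpoint is "Medication compliance (adherence, discontinuation, and persistence) by the number of non-pharmacological treatments". The test it names, for continuous variables, is ANOVA, or Kruskal-Wallis if variances are unequal. Its covariate line is "Covariates: antidepressant class covariates such as SSRIs, SNRIs, and other ADs will be used as grouping variables". It names no patient or provider characteristic and makes no reference to SAP 7.1.

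SAP 7.1 contains three relevant statements:
- On NPT: "Non-pharmacologic treatments will be used as a covariate if dependent variable is adherence, persistence, or discontinuation".
- On other variables: "Covariates will include variables such as age, geographic region, CCI score, and comorbidities".
- On the regression itself: "Also covariates in Table 3 will be included in multivariate logistic regression framework for each antidepressant choice".

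It also ties propensity-score methods to comparisons between antidepressants, and leaves the final variable list to be settled during analysis development. Table 3 lists provider specialty, class of clinic or hospital, region, psychiatric comorbidities and the Charlson index (CCI) as covariates. Its NPT codes cover psychotherapy, electroconvulsive therapy, psychiatric rehabilitation and psychiatric social work. SAP 4.1 sets no condition on prescriber specialty. Neither Table 3 nor 7.2.4 says over what period treatments are counted.

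**The concern.** Patients who receive psychiatric procedures are likely to be those treated in psychiatry, with more psychiatric comorbidity. If persistence or adherence differs between psychiatric and other care for any reason, a crude comparison by NPT number picks up that difference. Drug class, the one covariate listed, is not the variable that separates these settings. In a claims database even a small difference of this kind can reach p<0.05, the threshold in Protocol 9.7, and could then be reported as a link between NPT and compliance.

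The missing counting window is a second problem. If treatments are counted while compliance is accruing, patients who stay on drug longer have more time to receive them, and the count rises with the outcome.

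**Working it through.** The plan gives no sample size, power or effect size for 7.2.4, so there is no figure to reproduce. The checks below ask what the named comparison does when the true NPT effect is zero.

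**Assumed inputs (not in the documents).** Persistence SD 60 days; 60% of patients treated in psychiatry; three NPT levels (none, low, high) with shares 60/25/15% outside psychiatry; the share with none 10 or 20 points lower in psychiatry, split equally over the other two levels; persistence 5 to 20 days longer in psychiatry.

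**Sample sizes.** 10,000, 50,000 and 225,657. The last scales the earlier cohort in Protocol 9.5 to the 18-month intake: 752,190 × 1.5/5 = 225,657. It ignores the SAP's upper age limit of 70.

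**Step 1: spurious difference, 10-day gap, 20-point NPT gap.** Psychiatric shares by NPT level are:
- none: 0.6×0.40 / (0.6×0.40 + 0.4×0.60) = 0.24/0.48 = 0.500
- low: 0.6×0.35 / (0.6×0.35 + 0.4×0.25) = 0.21/0.31 = 0.677
- high: 0.6×0.25 / (0.6×0.25 + 0.4×0.15) = 0.15/0.21 = 0.714

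Multiplying by 10 days gives means 5.00, 6.77 and 7.14 above the non-psychiatric mean. The differences from none are 1.77 and 2.14 days, with no NPT effect at all.

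**Step 2: rejection rate.** Noncentrality λ = N × Σw(μ−μ̄)² / σ². Here Σw(μ−μ̄)² = 0.48×1.00² + 0.31×0.774² + 0.21×1.143² = 0.940, and σ² = 3,600 + 23 = 3,623. So λ = 2.59, 12.97 and 58.6 at the three N. The noncentral F distribution with 2 numerator degrees of freedom gives:

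| Specialty gap, NPT gap | Spurious difference (days) | N=10,000 | N=50,000 | N=225,657 |
|---|---|---|---|---|
| 5 days, 10 points | 0.44–0.56 | 0.06 | 0.12 | 0.39 |
| 10 days, 20 points | 1.77–2.14 | 0.28 | 0.91 | 1.00 |
| 20 days, 20 points | 3.55–4.29 | 0.82 | 1.00 | 1.00 |
| no gap | 0 | 0.05 | 0.05 | 0.05 |

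In simulation Kruskal-Wallis behaves like ANOVA (0.87 against 0.92 at N=50,000, second row).

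**Step 3: the extreme case.** If NPT is nearly confined to psychiatry, the bias is larger. For any use against none, the share of the specialty gap that appears as an NPT effect is P(psychiatry | NPT) − P(psychiatry | no NPT). With 60% psychiatric, and 30% NPT use there and none elsewhere, this is 1 − 0.42/0.82 = 0.49: 4.9 days for a 10-day gap and 9.8 for a 20-day gap. With 10% use elsewhere it is 0.18/0.22 − 0.42/0.78 = 0.28, or 2.8 days for a 10-day gap.

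**Step 4: does drug class help?** Take SSRI shares of 55% in psychiatry and 40% elsewhere. Within SSRI users the Step 1 shares become 0.132/0.228 = 0.579, 0.1155/0.1555 = 0.743 and 0.0825/0.1065 = 0.775. The spurious differences are 1.64 and 1.96 days, hardly changed. At N=50,000 simulated rejection within SSRI users is 0.50, lower mainly because the stratum holds 0.6×0.55 + 0.4×0.40 = 49% of patients. A model adjusted for class alone rejects in 0.90 of runs. Adding specialty brings rejection to 0.025–0.07 in every simulated scenario.

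**Step 5: counting window.** Adjustment alone is not enough. In a simulated null case (60% psychiatric, 30% of them NPT users, SD 60), with one quarter of NPT accrual depending on time on drug, a regression adjusted for class and specialty rejects in 80% of runs at N=2,000 and 100% at N=10,000. It shows about +5 days per treatment.

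**The case against.** Much of the case on the other side stands, and it limits the point.

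- **A test blind to NPT.** A reader might infer from the grouping-variable line that compliance is compared across drug classes and NPT is never tested. The documents do not support that. The title, aim, endpoint and stated role of 7.2.4 all name NPT, and the class line is a template bullet repeated in 7.2.1 to 7.2.5. It appears even in 7.2.5, where the grouping is by specialty.
- **No test for binary endpoints.** SAP 7.1 provides for tests suited to the distribution of the measure, with chi-square as an example. Adherence and discontinuation therefore have a test, though an unadjusted one.
- **No adjustment anywhere.** SAP 7.1 does foresee a compliance model with NPT beside age, region, CCI and comorbidities. What is missing is a link from 7.2.4, a regression stated for compliance outcomes, and a fixed variable list.
- **The missing regression sentence.** 7.2.4 is the only 7.2 subsection without one, but elsewhere that sentence models drug choice. Its absence is not itself a defect.
- **Specialist focus.** Protocol 9.9 says the study focuses on prescriptions by mental-health specialists. If that governs 7.2.4, most of the specialty confounding goes. SAP 4.1 does not impose it, and comorbidity and hospital class would stay unadjusted.
- **No causal claim.** SAP section 3 states no hypotheses, and the role of 7.2.4 is to inform. A real crude association is not a type I error as such. It misleads if read as the contribution of NPT, a reading invited by 7.1, which cites an earlier report that NPT increases adherence.

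**Conclusion.** The concern holds in limited form. As written, 7.2.4 yields a crude comparison that can reflect prescriber and comorbidity differences, and stratifying by drug class does not cure this. SAP 7.1 points towards an adjusted model but does not specify it for this question.

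The size is unknown from the documents. Under the assumed inputs the spurious difference is about 0.4 to 4.3 days when NPT occurs in both settings, and nearer 5 to 10 days only if it is confined to psychiatry. All rejection rates rest on the assumed specialty gap, NPT use, SD and N, and show direction and order of size only. At large N the main harm is a p-value that looks decisive beside a modest, biased difference. The analysis is secondary and exploratory, so severity is low to moderate.

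**What to change.** In SAP 7.2.4:

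1. Keep means, proportions and the ANOVA, Kruskal-Wallis or chi-square comparisons by NPT number, labelled descriptive.
2. Make the main result a regression of each compliance endpoint on NPT number: logistic for adherence and discontinuation, linear with robust standard errors for persistence days. Adjust for index drug or class, provider specialty, class of clinic or hospital, region, age, sex, CCI and baseline psychiatric comorbidities. Report the NPT estimate with its 95% CI.
3. Count NPT in a fixed window that ends before the compliance period analysed. The objective already has this structure for visit frequency: first 3 months against maintenance at months 4 to 9. Alternatively, treat NPT as time-dependent in a time-to-event model. The window must be set per endpoint: SAP 5.1 measures discontinuation within the first 90 days, so a 90-day window would overlap it completely.
4. Repeat within psychiatric prescribers as a check, and state whether the focus in Protocol 9.9 applies to this analysis.

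The cost is SAP wording and a few models on variables already in Table 3; no new data are needed. A landmark drops patients who stop before it, and the adjusted estimate will probably be smaller and less precise than the crude contrast.
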